Take One ezetimibe pill and 1-2 pills of Slo-niacin (or half of the daily dose indicated on the bottle) as instructed, with breakfast.

Evening/Night Dosing Directions (PM):

Take 1-2 Atorvastatin pills with dinner, as indicated on the bottle. Take 1-2 pills of Slo-niacin (or half of the daily dose indicated on the bottle) with dinner or before bed.

Valuable Information:

Niacin can sometimes cause a flushing feeling when you first start taking it. If this occurs, there are a few suggestions to help stop or reduce this feeling. The flushing feeling usually goes away over time if you continue to take niacin.

Some helpful ideas for reducing niacin-related flushing:

1. Take your medication in the morning and right before bed.
2. If you use a daily aspirin, take it 30 minutes before your niacin (either morning or evening). Do not take more than 325 mg Aspirin daily without first talking to your doctor.
3. 'Flushing' is reduced by food in your stomach. Enjoy a low-fat snack before you take niacin. An ounce of cheese with a few crackers, a cup of milk or yogurt with fresh fruit are a few examples.
4. Avoid hot drinks, alcohol and spicy foods with dinner as this can sometimes encourage flushing from niacin.

The study medication dispensing process is described under B.11.

B.9. Clinical and Laboratory Follow-up Procedures:

After randomization, the study subjects will be seen monthly for six months and bi-monthly for the remaining 30 months of the 36-month protocol. A total of 22 visits will be conducted for this study as shown in the procedure table below. This clinic visit protocol is developed based on the successful FATS and HATS (RO1 HL49546) clinic visit models. The clinical visits will be done by a team of investigators, coordinators and nurses as well at each of 3 study sites.

Participants who complete the first 3 years of the study and are willing to continue on the randomized therapy and will be followed every 4 months for up to 11 more years.

Table. Clinical Follow-up Protocol

Visit	Entry Criteria	Con-sent	Med. Hx	Family Hx	Vital Signs	Diet Counseling	AE/ Side Effects	Drug Disp.	Com-pliance	Safety Moni-toring	Meds Adj.
Screening	X	X			X						
Baseline		X	X	X	X	X		X			
Non-blood draw visits*					X	X	X	X	X	X	X
Blood draw visits**					X	X	X		X	X	

*: C1, 2, 4, 6, 10, 14, then every 4 months up to C130. **: C3, 5, 8, 12, then every 4 months up to C132.

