At these visits, subjects will undergo questioning about side effects and symptomatic state, and vital signs will be taken. At approximately 60% of the visits, blood will be drawn (<50 ml). The Table below provides the laboratory parameters collected/measured in this study.

Table. Laboratory Measurement Schedule for the Carotid Plaque Composition Study

Visit	S C R.	C o	C 3/ 5/ 8	C 12	C 16/ 20	C 24	C 28/ 32	C 36	Non-annual Visits C40/44/52/56/64 /68/76/80/88/92 /100/104/112/116 /124/128	Annual Visits C48/60/ 72/84/96/ 108/120/132	T X
TC/TG/LDL/ HDL/VLDL	X	X	X	X	X	X	X	X	X	X	X
HDL2&3/IDL/ LDLT/HDLT		X		X		X		X		X	
ApoB, A1, A2, ApoE, Lp(a)	X	X		X		X		X		X	
AST/ALT, CPK		X	X	X	X	X	X	X	X	X	X
BILI/ ALK PHOS/T4/TSH		X									
Creatinine/ Uric Acid		X		X		X		X		X	

Fasting glucose/ HbA1C**	X	X	X	X	X	X	X	X	X	X	X
Insulin/ Fibrino./ HsCRP		X		X		X		X		X	
Plasma storage		X		X				X		X	

*: SCR=screening; Co = baseline; C3, 10, 24, 36,..... = 3, 10, 24, 36,..... months in the study. TX = test for possible side effects of the study treatment. **: This schedule is for diabetic subjects. For non-diabetic patients fasting glucose is measured at S, Co, C12, C24, C36, C48, C60, and every 12 months up to C132.

Dietary counseling will be targeted at weight reduction with goals based on the level of obesity, with additional emphasis on the use of mono-unsaturated fats in a fat-limited (25-30%) diet. Dietary counseling will be provided to subjects by a certified research dietitian.

One week in advance of the next scheduled visits, subjects will receive a form letter from the study coordinators reminding them of the date and time, whether to fast, and to return unused drug supplies. One or two days before the visit they will again be reminded by telephone call from research assistance or the study coordinators, and the visit confirmed or changed. All scheduling is initiated by a computer program with capability to shift dates, making the associated adjustments in compliance calculations and drug distribution. Each clinical visit will take about 30 minutes.

B.10. Study Medication Dispensing

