- (1) Compare current results to baseline or previous values. This helps the investigators determine whether or not study medications could be the possible cause of the abnormal lab value.
- (2) Be thorough in evaluation of patient's side effects and confirm no other changes in life style or other medications could be the cause of such lab value change.
- (3) Determine if the result is only slightly elevated (less than 1.5 x Upper Limit of Normal (ULN) or glucose < 160 mg/dl), monitor patient closely and repeat the test at the next visit usually within 2-4 months per protocol.
- (4) If the result is 1.5-2.5 x ULN ALT/AST or CPK (or glucose ≥ 160 mg/dl), a repeat blood draw will be ordered within 1 month and subject will be closely monitored by telephone follow-up. Subject's primary care physician will be notified and patient will continue the study medications.

(5) If the result is $\geq 3 \times$ ULN ALT/AST or CPK, a repeat blood draw will be ordered within 2 weeks and subject's primary care physician will be notified, the study medications will be reduced or stopped, patient will be monitored closely by telephone follow-up and repeat lab test(s) will be ordered until the values normalize. If glucose >200 mg/dl, home glucose monitoring will be ordered and niacin will be reduced to half dose. If >240 mg/dl, home glucose monitoring will be ordered and niacin will be stopped until glucose levels return to <160 mg/dl.

Steps 3-5 are also outlined in the Table below for Lab Safety Monitoring.

Lab Safety Monitoring Protocol in CPC

	Sample at 3 months		Sample at 5 months		Sample at 8 months and all blood draw visits thereafter	
	Condition	Strategy	Condition	Strategy	Condition	Strategy
AST ALT CPK Safety:	If $<1.5X$ ULN	Careful Monitoring & repeat test @ C5	If $<1.5X$ ULN	Careful Monitoring & repeat test @ C8	If $<1.5X$ ULN	Careful Monitoring & repeat test @ C12
	If 1.5-2.5X ULN	Monitoring. Letter to PCP & repeat test within 1 M	If 1.5-2.5X ULN	Monitoring. Letter to PCP & repeat test within 1 M	If 1.5-2.5X ULN	Monitoring. Letter to PCP & repeat test within 1 M
	If $>3.0X$ ULN	Monitoring. Letter to PCP & repeat test within 2 Wk. Lower or stop meds	If $>3.0X$ ULN	Monitoring. Letter to PCP & repeat test within 2 Wk. Lower or stop meds	If $>3.0X$ ULN	Monitoring. Letter to PCP & repeat test within 2 Wk. Lower or stop meds

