Glucose Safety:	If 126-159 mg/dl	Careful monitoring	If 126-159 mg/dl	Careful monitoring	If 126-159 mg/dl	Careful monitoring
	If ≥ 160 mg/dl	Letter to PCP & repeat test within 1 M	If ≥ 160 mg/dl	Letter to PCP & repeat test within 1 M	If ≥ 160 mg/dl	Letter to PCP & repeat test within 1 M
	If >200 mg/dl	Repeat test within 2 Wk. Half niacin dose	If >200 mg/dl	Repeat test within 2 Wk. Half niacin dose	If >200 mg/dl	Repeat test within 2 Wk. Half niacin dose
	If >240 mg/dl	Glucose monitoring & stop niacin	If >240 mg/dl	Glucose monitoring & stop niacin	If >240 mg/dl	Glucose monitoring & stop niacin

ULN=Upper Limit of Normal

In addition, the following Table (**Dosage Adjustment Protocol for CPC**) provides basic guidance for dosage adjustment related to both reaching LDL-C and HDL-C targets and dealing with potential drug side effects.

Dosage Adjustment Protocol for CPC (Updated 01Aug2010)

	Sample at 3 months		Sample at 5 months		Sample at 8 months		Sample at 12 months and all visits thereafter	
Single	Target	Strategy	Target	Strategy	Target	Strategy	Target	Strategy
			If >80 ,		If >80 ,		If >80 ,	

Rx Group:	LDL-C ≤ 80 mg/dl	--	LDL-C ≤ 80 mg/dl	double statin dose, or (max dose 80mg)	LDL-C ≤ 80 mg/dl	double statin dose, or (max dose of 80mg)	LDL-C ≤ 80 mg/dl	double statin dose, or (max dose 80mg)
Double Rx Group:	LDL-C ≤ 80 mg/dl	--	HDL-C+5 from base.	Improve compliance	HDL-C+8 from base.	Improve compliance	HDL-C+10 from base.	Improve compliance
	--	--	LDL-C ≤ 80 mg/dl	If >80 mg/dl, double statin dose, or (max. dose 80 mg)	LDL-C ≤ 80 mg/dl	If >80 mg/dl, double statin dose, or (max. dose 80 mg)	LDL-C ≤ 80 mg/dl	If >80 mg/dl, double statin dose, or (max. dose 80 mg)
Triple Rx Group:	--	--	HDL-C+5 from base.	Improve compliance	HDL-C+8 from base.	Improve compliance	HDL-C+10 from base.	Improve compliance
	LDL-C ≤ 60 mg/dl	--	LDL-C ≤ 60 mg/dl	If >60, double statin dose, or (max. dose 80)	LDL-C ≤ 60 mg/dl	If >60, double statin dose, or (max. dose 80)	LDL-C ≤ 60 mg/dl	If >60, double statin dose, or (max. dose 80)
LDL Safety:	If SX/LCF or LDLC < 25	Half statin dose or stop meds	If SX/LCF or LDLC < 25	Half statin dose or stop meds	If SX/LCF or LDLC < 25	Half statin dose or stop meds	If SX/LCF or LDLC < 25	Half statin dose or stop meds

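### Non-diabetics have no scheduled glucose between baseline and month 12, while niacin is raised to 2 g/day; adding the assay to the existing C3, C5 and C8 draws is a cheap safety gain.

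*Combined protocol and SAP*

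**What the plan says.** **Who is tested, and when.** The Laboratory Measurement Schedule in B.9 marks fasting glucose and HbA1c at every draw, but its footnote then splits the population. Of the full row it says "This schedule is for diabetic subjects". For everyone else it says "For non-diabetic patients fasting glucose is measured at S, Co, C12, C24, C36, C48, C60, and every 12 months up to C132". The row also has a for-cause column: "TX = test for possible side effects of the study treatment".

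**When blood is drawn.** The footnote to the Clinical Follow-up Protocol gives the blood-draw visits as "C3, 5, 8, 12, then every 4 months up to C132". Lipids, AST/ALT and CPK are measured at C3, C5 and C8 in all subjects.

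**What is done with a result.** The Lab Safety table in C.3 has columns for 3 months, 5 months, and "Sample at 8 months and all blood draw visits thereafter". Its glucose rows apply the same thresholds in each column. A result of 160 mg/dl or more leads to a letter to the primary care physician and a repeat within a month. Above 200 the action is "Repeat test within 2 Wk. Half niacin dose"; above 240 it is "Glucose monitoring & stop niacin". Step 5 of the C.3 text agrees: "If >240 mg/dl, home glucose monitoring will be ordered and niacin will be stopped until glucose levels return to <160 mg/dl". Neither the text nor the table restricts these rules to diabetics.

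**Niacin dose.** B.7 starts at 500 mg/day and reaches 1,500 mg at month 2 and 2,000 mg at month 3. It allows up to 6 months for subjects who tolerate it less well.

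**The concern.** B.8 names raised blood sugar as a possible effect of niacin, in the same sentence as mildly abnormal liver tests. The liver tests are done in everyone at C3, C5 and C8; glucose is not. The rules for halving or stopping niacin therefore receive no routine result from non-diabetics during the whole escalation, or during the first months at full dose.

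This is a matter of subject safety in the double and triple therapy groups. B.8 also tells subjects, in its atorvastatin paragraph, that blood sugar is checked frequently. For a non-diabetic, the first on-treatment year contains one scheduled check.

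**Working it through.** The plan states no figure to reproduce. The check sets the draw schedule against the glucose schedule and the niacin titration.

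**Inputs**
- Blood draws: C3, C5, C8, C12, then every 4 months to C132 (B.9, follow-up table footnote).
- Glucose in non-diabetics after baseline: C12, then every 12 months to C132 (B.9, laboratory table footnote).
- 2 g/day reached at month 3 on standard titration, month 6 at the latest (B.7).
- Glucose thresholds: 126, 160, 200 and 240 mg/dl (C.3 table).

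**Step 1: draws with a scheduled glucose, non-diabetics**

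| Period | Draws | With glucose | Without |
|---|---|---|---|
| Before C12 | 3 | 0 | C3, C5, C8 |
| To C36 | 10 | 3 | 7 |
| To C132 | 3 + [(132 − 12)/4 + 1] = 34 | 132/12 = 11 | 23 |

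From C12 to C132 alone there are 31 draws. Of these, 31 − 11 = 20 carry no scheduled glucose for non-diabetics.

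**Step 2: time at 2 g/day before the first scheduled glucose at that dose**

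Under the present schedule this is 12 − 3 = 9 months (standard) or 12 − 6 = 6 months (slowest). With glucose added at C3, C5 and C8:

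| 2 g/day reached at month | Next draw | Months at 2 g/day |
|---|---|---|
| 3 | C5 | 2 |
| 4 | C5 | 1 |
| 5 | C8 | 3 |
| 6 | C8 | 2 |

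The range is 1 to 3 months. The first on-treatment glucose at any dose moves from month 12 to month 3. The longest first-year gap between on-treatment tests, counted from baseline, falls from 12 months to 12 − 8 = 4.

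**Step 3: rise needed to trigger a rule**

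I take below 126 mg/dl as a normal baseline, because that is where the table's lowest action band begins. The required rises are:
- to reach 160: more than 160 − 126 = 34 mg/dl;
- to pass 200: more than 200 − 126 = 74 mg/dl;
- to pass 240: more than 240 − 126 = 114 mg/dl.

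**Step 4: number affected**

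This cannot be computed. The documents give no share of non-diabetics and no glucose-specific rate. B.8 gives 2-4% of users as one figure across rash, raised blood sugar and abnormal liver tests. Suppose all of it were glucose, with 180 completers or 240 enrolled split equally over three arms. Then 120 × 0.02 to 120 × 0.04 is 2.4 to 4.8 niacin completers, and 160 × 0.02 to 160 × 0.04 is 3.2 to 6.4 enrolled. Those counts include diabetics and rises of any size.

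**The case against.** The strongest reply is that the plan chose this. The footnote sets out two tiers explicitly, and C.3 describes glucose testing as serving diabetes control. The drugs are approved, and C.1 rates the study as low risk. Exclusion 11 keeps out anyone with fasting glucose of 150 mg/dL or more, or HbA1c of 8% or more. This stands: the schedule is deliberate, and how often to test non-diabetics is partly clinical judgement. But no reason is given for leaving out the test during escalation, and niacin's effect on glucose is not described as confined to known diabetics.

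A reader might infer that the two tables contradict each other. They do not strictly do so. Each glucose row is conditional on a result, and the column headings are shared with AST/ALT and CPK, which everyone has. The rows can be read as acting on any glucose that happens to be available. What remains is that the table does not say whose samples it covers.

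A reader might also infer that a rise would be missed altogether. A rise that persists is seen at C12, so the finding is delayed detection. Symptom questioning at each visit and the for-cause test shorten the delay for subjects with complaints. They do not help with a rise without symptoms: C.3 alerts the safety monitor for symptoms that are severe at C1, or persistently moderate at three or more visits.

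Finally, the 150 mg/dL entry limit might suggest that rises of only 10, 50 or 90 mg/dl reach the thresholds. A value of 126-149 at screening or baseline is already abnormal by the table, and C.3 calls for abnormal results to be repeated. The uncovered group is the one that starts below 126.

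**Conclusion.** The point holds as a cheap safety improvement, not as an error in the plan. Non-diabetics on niacin have 0 of 3 draws before C12 with a scheduled glucose. A rise without symptoms from a normal baseline would go undetected until C12, after 6 to 9 months at 2 g/day.

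The number of subjects is unknown and probably small, given the rises needed to trigger dose changes and the 2-4% that B.8 spreads over three effects. The conclusion rests on reading the footnote literally, on taking 126 mg/dl as the upper edge of a normal baseline, and on applying C.3's repeat-test steps to abnormal baseline values.

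A reader might also infer a threat to the trial's main result. Nothing in the documents supports that: the carotid MRI analysis does not depend on when glucose is measured.

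**What to change.** **Schedule.** Amend the B.9 laboratory footnote so that non-diabetics also have fasting glucose at C3, C5 and C8, on blood already drawn. All arms is preferable, so that detection does not differ by arm; the two niacin arms is the minimum.

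**Table.** Add one sentence to the Lab Safety table: at non-annual draws after C12, the glucose rules apply to diabetics and to repeat or for-cause tests. If the sponsor keeps the present schedule, the same sentence should cover C3, C5 and C8. That costs nothing but leaves the gap open.

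**Cost.** There is no new visit or draw. The extra assays number at most 3 per non-diabetic; treating everyone as non-diabetic gives upper bounds:
- all arms: 3 × 180 = 540 for completers, 3 × 240 = 720 for all enrolled;
- niacin arms, assuming equal allocation: 3 × 120 = 360, or 3 × 160 = 480.

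Subjects would have to fast at these draws if they do not already; the documents do not say which draws are fasting. Some extra retests and niacin reductions would follow. The documents do not give enrolment status. If every subject is already past C12, only the table sentence still has an effect.

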(8) Subjects will be required to bring back all unused medications for compliance calculation. Unused medication will be returned to HMCIDS for destruction

C. Safety Monitoring and Procedures

C.1. Subject Safety and Monitoring Plan:

Objectives:

- (1) Monitor study progress and subject safety
- (2) Assure adverse event recording and reporting
- (3) Assure investigator communication with IRB and NHLBI
- (4) Assure protocol compliance
- (5) Assure data accuracy
- (6) Verification of initial study design and further modifications

Level of risk assessment: low level of risk

- (1) It is therapeutic study using all FDA approved drugs (Atorvastatin, Niacin, Ezetimibe).
- (2) Not an IND study
- (3) The study doesn't include vulnerable populations.
- (4) Study subjects are not at high risk, they are either with stable CAD or with sub-clinical atherosclerosis.

- (5) Primary endpoint of the study is carotid plaque lipid composition as assessed by MRI.

Safety monitoring will be provided by: study team

- (1) Investigators and study coordinators
- (2) Real time monitoring plan on management of risk to subjects
- (3) Annual review and report to IRB due to the lower level of risk

C.2. Safety Parameters:

- (1) Vital signs
- (2) Liver function: ALT/AST
- (3) Muscle enzyme: CPK
- (4) Fasting glucose levels

C.3. Safety Monitoring Procedures:

Clinical monitoring:

As discussed previously, at each of the clinical follow-up visits, subjects will undergo questioning about side effects and symptomatic state and vital signs will be taken. If any expected conditions or symptoms possibly related to the medications are reported as severe at C1 visit or persistently being moderate at ≥ 3 visits, the study safety monitor, [name], will be informed. Then, [name] will provide specific instructions on study medication change based on both his professional opinion and predefined monitoring protocol. For example, flushing and itching are most common side effects from niacin. In addition to a recommendation of taking aspirin 30 minutes prior taking niacin, taking niacin after dinner will further reduce these side effects, etc.

Laboratory monitoring:

There are three safety aspects we stress in this study: ALT/AST for liver function; CPK for muscle side effect; and glucose levels for diabetes control. If any of these is outside of the normal range, appropriate procedures will be taken:

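### As written, C.3 gives the safety monitor immediate notice of an expected, possibly drug-related symptom reported as severe only at the month-1 visit (C1); the wording is probably a slip for ≥ 1 visit

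*Combined protocol and SAP*

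**What the plan says.** The escalation rule is one sentence in C.3, under Clinical monitoring. It concerns expected conditions or symptoms that may be related to the study drugs. The safety monitor is informed if these "are reported as severe at C1 visit or persistently being moderate at ≥ 3 visits", and then gives specific instructions on changing study medication. The example that follows is flushing and itching on niacin: besides aspirin beforehand, "taking niacin after dinner will further reduce these side effects".

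The same paragraph has symptoms asked about throughout: "at each of the clinical follow-up visits, subjects will undergo questioning about side effects and symptomatic state". The clinical follow-up table in B.9 agrees. Its "AE/ Side Effects" column is marked for both blood-draw and non-blood-draw visits, and so is its safety-monitoring column.

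C1 is a visit code. The footnote to the B.9 follow-up table lists the non-blood-draw visits as "C1, 2, 4, 6, 10, 14, then every 4 months up to C130", and the footnote to the laboratory schedule explains that "C3, 10, 24, 36,..... = 3, 10, 24, 36,..... months in the study".

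**The concern.** The two limbs of the rule do not fit together. A symptom that is persistently moderate is escalated whenever it occurs, but a severe one is escalated at once only if reported at month 1. A subject who first reports a severe expected side effect at month 2, 12 or 30 does not meet the severe limb, although that is the more serious finding.

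The timing also suits the regimen poorly. At C1 a niacin subject has taken only the starting dose; the increases come at and after that visit. Up-titration of atorvastatin comes later still. Most dose increases therefore take effect after the only visit with a severe trigger.

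At stake is whether the person assigned to instruct on medication change hears of the symptom, and whether such cases are handled alike across sites. Detection of symptoms is not at stake.

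**Working it through.** **1. Reproduce the plan's visit count.** B.9 states 22 visits in the 36-month protocol: monthly for six months, then every two months for 30 months.

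- Follow-up visits by the text: 6 + 30/2 = 6 + 15 = 21.
- With baseline: 21 + 1 = 22, which matches.

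**2. Check against the B.9 footnotes, to month 36.**

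- Non-blood-draw: C1, 2, 4, 6, 10, 14, 18, 22, 26, 30, 34 = 11.
- Blood-draw: C3, 5, 8, 12, 16, 20, 24, 28, 32, 36 = 10.
- Total: 11 + 10 = 21, the same figure.

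**3. Apply the severe limb.**

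| | Visits with an immediate severe trigger | Visits without |
|---|---|---|
| As written (C1 only), to month 36 | 1/21 = 4.8% | 20/21 = 95.2% |
| If ≥ 1 visit was meant, to month 36 | 21/21 | 0/21 |

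**4. Extension visits, to C132.** The B.9 text has follow-up every 4 months: (132 − 40)/4 + 1 = 24 visits. The footnotes add non-blood-draw visits C38 to C130: (130 − 38)/4 + 1 = 24, for 48 in all. On either count, none carries the severe trigger as written.

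**5. Dose at C1.** B.7 starts niacin at 500 mg/day and steps to 1000, 1500 and 2000 mg at the month-1, month-2 and month-3 visits, taking up to 6 months if tolerance requires. At C1 the subject has taken 500/2000 = 25% of the full dose. B.6 begins atorvastatin up-titration at month 3; the dosage table begins it at month 5.

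**6. How far the persistence limb helps.** If moderate means at least moderate, a persistent severe symptom qualifies at its third visit. With visits two months apart (after month 6), that is at least 2 × 2 = 4 months after the first report. With visits four months apart in the extension, it is 2 × 4 = 8 months.

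**7. Other routes to the safety monitor.**

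- E.3 notifies the monitor of abnormal laboratory results. The laboratory schedule includes a test for possible side effects, so a symptom with a laboratory correlate could arrive that way. Flushing or itching need not.
- B.6 and the LDL safety rows of the dosage table allow the statin to be halved or medication stopped for symptoms. They do not mention the monitor.
- C.1 lists a "Real time monitoring plan on management of risk to subjects" run by the study team, with no notification trigger stated.

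**The case against.** The strongest reply is that the phrase is a slip. The parallel with ≥ 3 visits, the questioning at every visit and the niacin schedule all point to ≥ 1 visit. On that reading no visit is uncovered and the 20 of 21 describes only a literal reading. This stands as a limit on the consequence. It does not remove the need to correct the text, because staff can apply only what is written, and C1 is a valid visit code that can be followed literally. A misread character in the PDF text is possible, although the ≥ later in the same sentence came through.

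Second, the sentence covers expected, possibly drug-related symptoms and reads as a tolerability rule. It need not be the trial's whole adverse-event escalation, and the adverse-event record sheet (Attachment 2) is not in the available text. That stands, and the point is confined to this rule.

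Third, the persistence limb may catch a lasting severe symptom. That also stands, with the delay shown above, but it does nothing for a first or short-lived one.

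Fourth, a reader might infer that severe symptoms after month 1 go undetected or unmanaged. The documents do not support this. Besides the questioning at every visit and the C.3 advice on flushing, B.10 has a study doctor sign the prescription for each scheduled visit and an investigator review medication instructions at dispensing. Nor does the B.9 table, which marks medication adjustment only in the "Non-blood draw visits" row, show that no action is possible at blood-draw visits: B.6 and the dosage table set symptom-based statin rules at exactly those visits.

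Fifth, the dose argument is about niacin. Single-therapy subjects are already on their starting atorvastatin dose (20 to 80 mg) by C1, so for them only later up-titration is relevant.

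**Conclusion.** The point holds for the text as written and should be fixed. The immediate severe-symptom trigger applies at 1 of 21 follow-up visits to month 36 and at no extension visit. No other available section sends a first severe symptom after month 1 to the safety monitor unless it shows up as an abnormal laboratory result.

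The consequence is limited to notifying the person whom C.3 makes responsible for instructions on medication change. Two stronger inferences should not be drawn. The 95.2% is a share of visits, not of subjects, symptoms or risk; the documents give no rate of severe symptoms, so the number affected cannot be estimated. Nor can it be said that an independent or separate safety function is bypassed: C.1 assigns safety monitoring to the study team, and whether the monitor is distinct from the investigators who see subjects is not established.

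The conclusion rests on reading C1 as the visit code that B.9 makes it, and on the extracted text being faithful. Confidence is medium, because a slip is the likelier explanation and the source page has not been seen.

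**What to change.** Check the sentence against the source document. If it does read C1, change the severe limb so that it applies at ≥ 1 visit (any visit). Leave the moderate limb, the rest of the sentence and the safety monitor's role as they are. If the source already reads ≥ 1 visit, nothing needs changing.

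The cost is one phrase and a few extra notifications to an existing role. No visits, tests or staff are added.
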